### Descriptive variables

Variables collected for descriptive purposes are data on examination findings, pain intensity and duration, Peak Heigh Velocity, level of sports participation and anthropometrics

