## Background

Osgood-Schlatter is a growth-related condition involving multiple types of tissue in the tendon-bone interface at the tibial tubercle. Osgood-Schlatter affects one in ten adolescents causing persistent pain, reduced peak torque during knee extension, and reduced ability to maintain participation in sports and physical activity. Rate of torque development is linked to athletic performances, and reductions in rate of torque development is associated with decreased neuromuscular functioning and pain chronicity. As peak torque is reduced in Osgood-Schlatter, changes in rate of torque development is likely also affected, but this has not yet been investigated. This insight could help characterize the condition and guide management.

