## Methods

The study design and analysis strategy have been published along with a trial registration (ClinicalTrials.gov NCT05789095). The study will include 13 adolescent participants with Osgood-Schlatter and a group of 13 pain free controls matched on sex, age, and sports participation on the group level. Testing will include bilateral rate of torque development measurements of knee extension and flexion, with a fixated handheld dynamometer, during a single test-session lasting approximately two hours. The examiner responsible for strength-testing will be blinded to case-status. Along with anthropometric data, participants will perform the anterior knee pain provocation test to assess pain-response to sustained knee loading, a countermovement jump test to assess power and jump height, and provide patient-reported measures of condition severity, pain, disability, and quality of life. Data collection will start February 2023 and is expected to be completed by May 2023.

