## Methods

### Study design

In this study we will include adolescent participants with Osgood-Schlatter, presenting as anterior knee pain localized to the tibial tubercle (OSD-group), and a matched group of pain free controls (control group), matched on sex, age (<1 year group difference) and type of sports (weightbearing vs non-weightbearing). The study will be conducted at the International Olympic Research Center - Copenhagen (Sports Orthopaedic Research Centre - Copenhagen), at Hvidovre University Hospital. The project will be initiated March 2023, with recruitment of 26 participants: 13 participants in the OSD-group, and 13 in control group.

Approval has been obtained from the ethical review board of the Capital Region of Denmark (H-20072873), and the Data Management Agency of Capitol Region of Denmark (P-2021-73).

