#### Clinical examination and treatment

The study procedures will be conducted by two examiners (JL and HS). JL will be aware of the case status and conducts the screening and preliminary testing. To avoid bias, examiner HS will be blinded for the case status during trial and will not know the Numerical pain Rating Scale-scores (NRS, 0-10, 'no pain' to 'worst pain imaginable') of the participants during testing. To strengthen the inter-reliability, the examiners will not change roles during the study.

The session starts with JL examining the potential participant in the OSD-case group, for Osgood-Schlatter. If the Osgood-Schlatter diagnosis is made, the participant is then enrolled. For the potential participant in the control group, JL screens for potential injury or pain in relation to the knee joint. In the absence of relevant pathology, the control-participant is enrolled.

Then, JL measures length of the lever arm and variables for peak hight velocity assessment. Participants will then answer the patient-reported outcome measures together with their parent/guardian.

For the rate of force development tests, HS will enter the room and conduct the tests as described below. For each attempt the participant will write down their NRS-rating on a piece of paper, out of sight from HS.

Before the rate of force development test is conducted, the participants are told that they can always abort the test, if they perceive that pain rises to such a degree that they can't continue the

testing, or they start feeling fearful or uncertain of their symptoms. They are ultimately told that potential pain felt during testing are not harmful and will subside within 24 hours, as is our experience from multiple earlier conducted tests.

HS leaves the room, for JL to conduct the Anterior Knee Pain Provocation test and save the NRS results.

HS returns to conduct the Counter Movement Jump Test, again blinded for the participants NRS-scores, which are written down on a piece of paper. HS leaves the room, and JL either treats the patient (case-group) or hands out compensation for participating (control-group).

Cases and controls will be instructed not to take any pain medication 24 hours prior to any assessment to ensure that this does not affect measurements.

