### Statistical considerations

#### Sample size

No previous investigations of rate of torque have been published for adolescents with Osgood-Schlatter. One previous study using the same clinical test setup, equipment, and time-epochs (Early RTD: 0-100 ms, Late RTD: 0-200 ms, and peak RTD) for testing RTD over the hip in young (Under-19) professional soccer players found a mean of 9.57 Nm/kg/s and a standard deviation of 2.6 Nm/s/kg at 0-100 ms.

Considering that peak torque is around 30-50% lower for adolescents (U13 and U14) compared to U19 players, a similar difference might be expected for RTD, and thus we expect a group mean RTD of around 5 or 6 Nm/kg/s at 0-100 ms for asymptomatic adolescents. In adults with non-traumatic knee pain, investigations of RTD during maximal isometric hip extension, has shown differences between symptomatic participants and controls of >50 % during early RTD.

As this study includes RTD of the knee, which is the affected joint, we expect at least similar differences for our primary measure, early RTD at 0-100 ms, this would correspond for example to a between-group difference of 6 vs. 3 Nm/kg/s. We will assume 2.6 Nm/kg/s as an asymptomatic population standard deviation for 0-100 ms. Based on a two-sided two-sample t-test at 80% power and 5% alpha level, 13 participants in each group would thus be needed to detect a 50% between-group difference (R 4.0.2, Foundation for Statistical Computing, Vienna, Austria; RStudio 1.0.153, power.t.t.test package).

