## Statistical methods

The outcome variables (rate of torque development 0-100 ms, 0-200 ms, peak RTD, time to peak RTD, time to peak torque for both knee extension and knee flexion, respectively) will be compared between groups using an unpaired two-sided students t-test, assuming the residuals will be normally distributed, otherwise the non-parametric alternative, the Wilcoxon rank sum test, will be used. The alfa and beta-1 level will be set for 5% and 80%, respectively.

As outcome variables have been a priori specified and prioritized, and also analyzed and reported in the pre-specified order, no corrections for multiple testing will be applied. Data will be reported with between-group differences, standardized effect sizes based on Cohens d, exact p-values, and 95% confidence intervals. All data inspection, analysis, and visualizations will be conducted using R (R Foundation for Statistical Computing, Vienna, Austria), in the jamovi interface (The jamovi project 2023, version 2.4.1). All r-code and full data set will be shared with journal publication or in an open-access repository.

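### Peak height velocity is collected but kept out of the group comparison, so a systematic maturity difference between cases and controls, if there is one, would bias hypotheses 1, 3, 4 and 6

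*Combined protocol and SAP*

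**What the plan says.** All references are to the combined protocol and SAP.

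- **Condition.** Background states: "Osgood-Schlatter is a growth-related condition involving multiple types of tissue in the tendon-bone interface at the tibial tubercle".
- **Matching.** Study design has controls "matched on sex, age (<1 year group difference) and type of sports (weightbearing vs non-weightbearing"). The Methods summary near the front adds that participants are "matched on sex, age, and sports participation on the group level". Maturity is not a matching factor.
- **Measurement.** Under Clinical examination and treatment, after a case or a control is enrolled and before strength testing, the unblinded examiner "measures length of the lever arm and variables for peak hight velocity assessment". Nothing restricts this to one group.
- **Use.** Descriptive variables gives the role: "Variables collected for descriptive purposes are data on examination findings, pain intensity and duration, Peak Heigh Velocity", with sports level and body measurements after it.
- **Analysis.** Under Statistical methods the outcomes "will be compared between groups using an unpaired two-sided students t-test, assuming the residuals will be normally distributed", with the rank sum test as fallback. There are no covariates and no sensitivity analysis for maturity.
- **Interpretation.** Expected results and implications names the comparison of main interest: RTD in symptom-free limbs, or in flexion, against controls. A reduction there would be taken as a sign of central inhibition of neuromuscular function.

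**The concern.** Cases are selected on a condition that the plan ties to growth. Controls are selected on calendar age, sex and sport type. Adolescents of the same age and sex can stand at different points around peak height velocity, and eligibility runs from 9 to 16 years. Matching on age therefore does not guarantee that the groups are alike in maturity, and a group-level tolerance of just under one year is loose even for age.

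The plan itself expects strength to rise with development. Its sample-size argument begins "Considering that peak torque is around 30-50% lower for adolescents (U13 and U14) compared to U19 players" and carries this over to RTD already expressed per kilogram. On the plan's own reasoning, dividing by body weight does not remove the developmental gradient.

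A maturity difference would act on both legs and on both movements. That is what the plan would read as central inhibition, so hypotheses 3, 4 and 6 are the most exposed. Hypothesis 1 is affected too. Hypotheses 2 and 5 compare two knees of the same person and are not affected.

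**Working it through.** **1. The plan's own figure.** Inputs from Sample size: difference 6 - 3 = 3 Nm/kg/s, SD 2.6, two-sided 5%, 80% power.
- Standardised difference: 3/2.6 = 1.154.
- The noncentral t gives n = 12.83, so 13 per group, with power 80.6% on 24 degrees of freedom. The stated 13 reproduces.
- Standard error of the difference: 2.6 x sqrt(2/13) = 1.020.

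**2. Bias of the unadjusted test.** Two inputs are missing from the documents and are assumed: the maturity gap g, in SDs of maturity, and the within-group maturity-RTD correlation r. With total within-group SD held at 2.6:
- bias = r x g x 2.6 Nm/kg/s
- noncentrality with no true case-control difference = bias/1.020

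| Gap (SD) | Correlation | Bias | Share of 3 | Noncentrality | False rejection, unadjusted |
|---|---|---|---|---|---|
| 0.5 | 0.3 | 0.39 | 13% | 0.38 | 6.6% |
| 0.5 | 0.5 | 0.65 | 22% | 0.64 | 9.4% |
| 0.5 | 0.6 | 0.78 | 26% | 0.76 | 11.4% |
| 0.75 | 0.5 | 0.975 | 32.5% | 0.96 | 15% |

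The less favourable corner, gap 0.75 with correlation 0.6, gives bias 1.17, noncentrality 1.15 and about 20%. With maturity as a covariate, simulated false rejection stays at about 5% throughout.

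**3. The opposite direction.** If cases are more mature, a true difference of 3 shrinks. At a 0.5 SD gap the unadjusted noncentrality is (3 - 0.39)/1.020 = 2.56 at correlation 0.3 and (3 - 0.78)/1.020 = 2.18 at 0.6. Power is then 69% and 55%, against 80.6% planned.

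**4. Price of adjusting.** With one covariate (23 degrees of freedom), the variance of the adjusted difference is

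2.6² x (1 - r²) x (2/13 + D²/Sxx),

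where D is the observed maturity difference and Sxx the pooled within-group sum of squares of maturity. The second term is the collinearity cost and grows with the gap. At r = 0 and a true gap of 1 SD, the mean of D² is 1 + 2/13 = 1.154 and the mean of 1/Sxx is 1/22. The standard error is about 2.6 x sqrt(0.154 + 0.052) = 1.18, the noncentrality 3/1.18 = 2.54, and power about 68%. Simulation gives 69%. Simulated adjusted power for a true difference of 3:

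| Gap (SD) | r = 0 | r = 0.3 | r = 0.5 |
|---|---|---|---|
| 0 | 78-79% | 82% | 89% |
| 0.5 | 76% | 80% | 87% |
| 0.75 | 73% | 77% | 84% |
| 1 | 69% | 73% | 81% |

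With no gap and r = 0.6, power is 93%.

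**5. A raw-scale illustration only.** Spreading the plan's 30-50% deficit from 9.57 over an assumed 5 years gives 9.57 x 0.30/5 = 0.57 to 9.57 x 0.50/5 = 0.96 Nm/kg/s per year, or 19-32% of 3. This is a calendar-age gradient. It combines hip RTD in professional under-19 players with a peak-torque ratio, and it is not a maturity slope at fixed age.

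**The case against.** The strongest reply is that no gap has been shown. A reader might infer from the growth-related label that cases will be less mature, and that the unadjusted test will therefore report a false deficit. The documents support neither step: no passage says that cases differ in maturity from controls of the same age and sex, or in which direction. Imbalance arising purely by chance is already covered by the t-test's standard error. Only a systematic difference causes bias. This objection stands, and it makes the point conditional.

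A second reply concerns size. At a 0.5 SD gap and correlation 0.3, false rejection is 6.6%, which is small. The assumed correlations also include whatever age contributes in a 9-16 year sample, so neither the bias nor the precision figures can be credited to maturity at fixed age alone. Reading 19-32% as the effect of one year of maturity would make the same mistake. This stands too.

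Third, adjustment has a cost. It is tempting to call it one degree of freedom, but that holds only when the groups are balanced. With a gap, adjusted power can drop below the planned 80%.

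Fourth, the plan has partial safeguards: normalisation to lever arm and body weight, matching, descriptive reporting of peak height velocity, and sharing of data and code. These reduce the problem without closing it. By the plan's own figures the gradient survives division by weight. A descriptive table shows an imbalance but not its effect on the result, and an adjustment chosen after seeing the data would be post hoc.

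**Conclusion.** The point holds as a conditional one. The plan collects a plausible confounder for a growth-related condition, leaves it out of the comparison, and intends an interpretation that a maturity difference could imitate. If a systematic gap exists, hypotheses 1, 3, 4 and 6 are biased in a direction that cannot be stated in advance. For the combinations tabulated, false rejection is about 6.5-15% instead of 5%. All of this rests on an assumed gap, an assumed correlation and a linear maturity effect.

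Two stronger readings are not supported. The documents do not show that a gap will occur. Nor would maturity alone, at the tabulated values, produce the 50% deficit used for planning: the largest tabulated bias is 0.975, about a third of the difference of 3. The weight lies on the asymptomatic limb and on flexion, where a modest deficit would carry the study's main conclusion.

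**What to change.** - In Statistical methods, pre-specify a linear model with group and maturity offset (years from peak height velocity, derived from the variables already collected) for the RTD outcomes under hypotheses 1, 3, 4 and 6.
- Report the adjusted difference with its 95% confidence interval beside the unadjusted t-test or rank sum result.
- In Descriptive variables, state that peak height velocity also serves as a covariate, and report its mean and SD by group.
- State that a deficit in the asymptomatic limb or in flexion will not be interpreted as central inhibition unless it persists after adjustment.

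**Cost.** The change is one of wording, with no new measurement, and should be settled before outcome data are examined. With no gap, power is about 78-79% if maturity is unrelated to RTD, and 82-93% at correlations of 0.3-0.6. With a gap of 0.5-1 SD it is about 76-69% at correlation 0 and 80-73% at 0.3. Maturity offset is estimated with error, so some confounding may remain.

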### Statistical considerations

#### Sample size

No previous investigations of rate of torque have been published for adolescents with Osgood-Schlatter. One previous study using the same clinical test setup, equipment, and time-epochs (Early RTD: 0-100 ms, Late RTD: 0-200 ms, and peak RTD) for testing RTD over the hip in young (Under-19) professional soccer players found a mean of 9.57 Nm/kg/s and a standard deviation of 2.6 Nm/s/kg at 0-100 ms.

Considering that peak torque is around 30-50% lower for adolescents (U13 and U14) compared to U19 players, a similar difference might be expected for RTD, and thus we expect a group mean RTD of around 5 or 6 Nm/kg/s at 0-100 ms for asymptomatic adolescents. In adults with non-traumatic knee pain, investigations of RTD during maximal isometric hip extension, has shown differences between symptomatic participants and controls of >50 % during early RTD.

As this study includes RTD of the knee, which is the affected joint, we expect at least similar differences for our primary measure, early RTD at 0-100 ms, this would correspond for example to a between-group difference of 6 vs. 3 Nm/kg/s. We will assume 2.6 Nm/kg/s as an asymptomatic population standard deviation for 0-100 ms. Based on a two-sided two-sample t-test at 80% power and 5% alpha level, 13 participants in each group would thus be needed to detect a 50% between-group difference (R 4.0.2, Foundation for Statistical Computing, Vienna, Austria; RStudio 1.0.153, power.t.t.test package).

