## Aim

To investigate if early and peak rate of torque development during knee extension is reduced in the asymptomatic limbs or during knee flexion in adolescents with Osgood-Schlatter, compared to a matched group of asymptomatic adolescents.

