## Expected results and implications

As the condition affects the knee-extensor mechanism, we expect lower levels of rate of torque development in the affected knee during extension. The main interest, however, is if the level of rate of torque development is also significantly reduced in non-symptomatic limbs or in knee flexion, in cases compared to symptom-free healthy controls. This would indicate inhibited neuromuscular function on a central level, due to other factors than local tissue pathology, such as pain chronicity, central muscle inhibition, or other drivers.

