## Hypotheses

The hypotheses being tested are

1. that adolescents with Osgood-Schlatter, has a lower knee extension RTD in their affected knee compared to matched controls
2. that adolescents with Osgood-Schlatter, has a lower knee extension RTD in their affected knee compared to their potential asymptomatic knee
3. that adolescents with Osgood-Schlatter, has a lower knee extension RTD in their potential asymptomatic knee compared to matched controls
4. that adolescents with Osgood-Schlatter, has a lower knee flexion RTD in their affected knee compared to matched control
5. that adolescents with Osgood-Schlatter, has a lower knee flexion RTD in their affected knee compared to their potential asymptomatic knee
6. that adolescents with Osgood-Schlatter, has a lower knee flexion RTD in their potential asymptomatic knee compared to matched controls
7. That levels of either early or late rate of torque development is negatively correlated with pain during rate of torque development-testing, countermovement jump height or power, anterior knee pain provocation test score, current pain, pain duration, KOOS child 'Pain', 'Sport/rec' or 'QoL' subscales,

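### The plan names a primary measure (RTD 0-100 ms) but no primary limb and movement, and its sections disagree on which case-control contrast answers the question

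*Combined protocol and SAP*

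**What the plan says.** Four places bear on which comparison decides the study.

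- **Aim:** "To investigate if early and peak rate of torque development during knee extension is reduced in the asymptomatic limbs or during knee flexion", in cases compared with matched controls. Extension in the affected knee is not part of it.
- **Expected results and implications:** lower RTD in affected-knee extension is presented as the expected finding. Then: "The main interest, however, is if the level of rate of torque development is also significantly reduced in non-symptomatic limbs or in knee flexion". A reduction there is what the plan would read as inhibition at a central level.
- **Hypotheses:** seven are listed and none is labelled primary. The first is "that adolescents with Osgood-Schlatter, has a lower knee extension RTD in their affected knee compared to matched controls". Hypotheses 3, 4 and 6 are the other case-control contrasts: asymptomatic-knee extension, affected-knee flexion and asymptomatic-knee flexion. Hypotheses 2 and 5 compare knees within cases, and hypothesis 7 concerns correlations.
- **Sample size:** a primary measure is named ("which is the affected joint, we expect at least similar differences for our primary measure, early RTD at 0-100 ms"), with no limb or movement attached.

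Statistical methods says that the outcome variables are prioritised and reported in a set order, and on that ground applies no multiplicity correction. The order given there is RTD 0-100 ms, RTD 0-200 ms, peak RTD and two time-to-peak variables, each for extension and flexion. The affected and asymptomatic limbs are not mentioned.

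**The concern.** The candidate contrasts answer different questions. A deficit confined to affected-knee extension is what local tissue pathology predicts, and the plan already expects it. A deficit in another limb or in flexion is the finding that the plan would interpret as central. If the hypothesis order is followed, the leading contrast is one that the aim omits. If the aim is followed, the leading contrast is one of three joined by an unranked 'or'. Nothing in the document settles the choice, so it can be made after the results are known, and any one of the contrasts could be put forward as the study's answer.

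**Working it through.** **1. Setting the sections side by side**

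| Section | Limb and movement put forward | RTD variable |
|---|---|---|
| Aim | asymptomatic limbs (extension), or flexion | early and peak |
| Expected results | non-symptomatic limbs, or flexion, as main interest; affected-knee extension as expectation | not specified |
| Rationale and background | RTD effect in general first; non-affected leg as a further suspicion | not specified |
| Hypotheses | affected-knee extension first; no label | not specified |
| Sample size | the knee as affected joint; no limb or movement | 0-100 ms primary |
| Statistical methods | extension and flexion; no limb | 0-100 ms first, peak third |

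No row supplies measure, limb and movement together. The Aim and Hypotheses rows lead to different contrasts.

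**2. Reproducing the stated sample size**

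Inputs, all from Sample size: "Based on a two-sided two-sample t-test at 80% power and 5% alpha level"; "a between-group difference of 6 vs. 3 Nm/kg/s"; "We will assume 2.6 Nm/kg/s as an asymptomatic population standard deviation for 0-100 ms".

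- Standardised difference: d = 3 / 2.6 = 1.154.
- Two-sample t-test with the noncentral t distribution: n = 12.83 per group, rounded up to 13.
- At 13 per group: noncentrality = 1.154 × √(13/2) = 2.94 on 24 degrees of freedom, power 80.6%.

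The stated figure, "13 participants in each group would thus be needed to detect a 50% between-group difference", is reproduced.

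**3. What 13 per group gives if a main-interest contrast is primary**

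The documents give no effect size specific to the asymptomatic limb or to flexion, so smaller deficits are assumed, from a control mean of 6 and SD 2.6.

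| Deficit | Difference | d | Power at 13 per group | n per group for 80% |
|---|---|---|---|---|
| 50% | 3.0 | 1.154 | 80.6% | 13 |
| 40% | 2.4 | 0.923 | 61.7% | 20 |
| 30% | 1.8 | 0.692 | 39.5% | 34 |
| 25% | 1.5 | 0.577 | 29.2% | 49 |

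Hypotheses 3 and 6 use only cases who have an asymptomatic knee. That number is not given. With m such cases against 13 controls, noncentrality = 1.154 / √(1/m + 1/13). For a full 50% deficit:

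- m = 10: 2.74, power 74.4%
- m = 8: 2.57, power 68.3%
- m = 6: 2.34, power 59.7%

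**4. How often the two readings disagree**

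This was simulated with 40,000 studies per setting: 13 per group, equal SDs, four correlated measures per person (assumed correlation 0.3 to 0.8), and all 13 cases contributing an asymptomatic knee. A contrast counts as positive if it shows a reduction significant at two-sided 5%. Hypothesis 1 carries the 50% deficit throughout. Disagreement means that hypothesis 1 and the set of hypotheses 3, 4 and 6 (any one positive) give different answers.

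| Deficit in hypotheses 3, 4 and 6 | Disagreement |
|---|---|
| none (purely local effect) | 74-75% |
| 25% | 36-38% |
| 50% | 13-20% |

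In the purely local row, hypothesis 1 is positive in about 80% of studies and at least one of the other three in 5-7%. Disagreement there is therefore mostly the power of hypothesis 1.

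**The case against.** **The sample size text may not favour hypothesis 1.** A reader might infer that the study was sized on affected-knee extension. The text does not say so. It speaks of the knee as the affected joint, which fits affected-knee flexion equally well, and its reference for a deficit above 50% is hip extension in adults with knee pain. This objection stands. The conflict rests on the aim and main interest against the hypothesis order, with the sample size text leaving the matter open.

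**The plan already limits what hypothesis 1 can show.** Expected results ties the central interpretation to the other limbs or flexion, so the document does not let a positive hypothesis 1 alone support it. That is fair. It does not say which of the remaining contrasts carries the conclusion, or whether one is enough.

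**This is a cross-sectional case-control study with no success criterion**, and it promises effect sizes, confidence intervals, exact p-values and shared data. That lowers the stakes. But the plan uses its prioritised order to justify leaving multiplicity uncorrected, and that order does not cover limb or movement.

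**A primary contrast may be named elsewhere.** Methods says that the design and analysis strategy were published with a registration. That material is not part of this document, so the point is confined to what this document says.

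**The early-and-peak wording is minor.** The aim puts early RTD first, consistent with the primary measure. Peak RTD needs only a secondary label.

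**Conclusion.** The point holds as a conflict over which contrast is primary. The document fixes RTD 0-100 ms but not the limb and movement, and its sections lead to different contrasts. The sample size of 13 per group is arithmetically correct.

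A reader might take the 74-75% disagreement as the chance of a wrong conclusion. It is not an error rate. In that scenario a positive hypothesis 1 with the others negative is the right answer to two different questions. The figure falls to 36-38% or 13-20% when the other contrasts carry a 25% or 50% deficit. All three rest on assumed correlations, equal SDs and 13 asymptomatic knees. The contradiction between sections stands without them.

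The figures that matter for the decision are the powers. If a main-interest contrast is primary, 80% holds only for a 50% deficit there. The smaller deficits and the counts of asymptomatic knees are assumptions, shown as a range. The plan should be corrected, although the remedy is mainly a matter of wording.

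**What to change.** In Sample size and Statistical methods, name one primary case-control contrast by limb, movement and window (0-100 ms), preferably one that matches the aim. Do this before any group comparison is seen. Label every other limb, movement and window, including peak RTD, as secondary. Align Aim, Expected results and Hypotheses with the choice, and justify the assumed deficit for that contrast.

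The options differ:

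- **Hypothesis 4** (flexion, affected knee) keeps all 13 cases. It tests the painful knee, and the rationale itself says that local pain may limit activation, so it separates central from local causes less cleanly.
- **Hypothesis 3 or 6** (asymptomatic knee) separates them better but uses only cases with such a knee. State how many are expected.
- **Hypothesis 1** can stay primary if the aim is reworded to include it and the central-inhibition contrasts are labelled secondary.

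The edit needs no new measurements. Its cost is that the unnamed parts of the aim become secondary and that, for a main-interest contrast, the plan must either defend a 50% deficit, accept the lower power tabulated above, or recruit more participants.
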